## 7.4. Baseline Values

For both safety and non-safety evaluations, the baseline is defined as the last available assessment before receiving study drug. If there is no such value, the baseline will be missing.

## 7.5. Coded Terms and Used Dictionaries

Medical history and AEs will be coded using the Medical dictionary for regulatory activities (MedDRA).

All laboratory data will be converted to standard units and classified into CTC grades according to the NCI CTCAE by the data management.

Concomitant medications will be coded using the WHO Drug dictionary.

## 7.6. Handling/Classification of Concomitant Medication and Adverse Events

For phase I, each AE will be assigned to a cohort depending on the last dose administered before the AE onset. Thus, in case of dose modifications, different AEs of one patient can be reported under different cohorts. See the next section 7.7 for specification for handling of missing dates/times.

For phase II, the AEs will be reported based on disease cohort, thus further specific classification is not needed.

## 7.7. Methods for Handling of Incomplete Dates/Times

If the date of the original diagnosis/ the current relapse/ stop date of the last therapy has missing day, the 1st of the month will be imputed. In case of missing month and/or year, no imputation will be performed and the date will be considered as missing. No imputation will be performed for PK concentrations missing date or time data.

### 7.7.1. Phase I AEs

In case of missing dates/times, the more conservative approach will be taken as follows.

#### In case of missing time

If the date of the AE onset equals the date of drug administration and time of AE onset and/or drug administration is missing (thus it is not clear whether the AE should be assigned to the dose administered on the same day or to the previous dose), the AE is assigned to the lower non-zero dose. The situation is illustrated in the following table.

Day	D1MMMYYYY	D2MMMYYYY	Assigned dose cohort
Dose (mg)	x1	x2	D=min(x1,x2)
AE start date		? D2MMMYYYY	

#### In case of partial dates

If a year and a month of an AE onset are present and a day is missing, the AE will be assigned to the lowest non-zero dose administered during that month. If no non-zero dose was administered during that month, the AE will be assigned to the last dose administered during the previous month. If no dose was administered during the previous month, the AE will not be considered as treatment emergent (see the definition below). The situation is illustrated in the following table.

Month	M1	M2			Assigned dose cohort	
Day	N1	1	2	...	N2	If $x_{N1} = y_1 = \dots = y_{N2} = 0$ , then not TE AE
Dose (mg)	$x_{N1}$	$y_1$	$y_2$	...	$y_{N2}$	
AE start date		UNK M2 YYYY				If $x_{N1} \neq 0$ AND $y_1 = \dots = y_{N2} = 0$ , then $D = x_{N1}$
						If any $y_i \neq 0$ , then $D = \min(y_1, \dots, y_{N2})$

[figure not shown]
If only the year of an AE onset is present, the AE will be assigned to the lowest non-zero dose administered during that year. If no non-zero dose was administered during that year, the AE will be assigned to the last dose administered during December of the previous year. If no dose was administered during December of the previous year, the AE will not be considered as treatment emergent (see the definition below). The situation is illustrated in the following table.

Year	Y1	Y2				Assigned dose cohort
Month	Dec	Jan	Feb	...	Dec	If $x_{N1} = y_1 = \dots = y_{N2} = 0$ , then not TE AE
Dose (mg)	$x_{N1}$	$y_1, y_2, \dots, y_{N2}$				
AE start date		UNK UNK YYYY				If $x_{N1} \neq 0$ AND $y_1 = \dots = y_{N2} = 0$ , then $D = x_{N1}$
						If any $y_i \neq 0$ , then $D = \min(y_1, \dots, y_{N2})$

[figure not shown]
### 7.7.2. Phase II AEs

The following approach applies to AEs in phase II. In case of missing dates, the start dates of the events will be imputed in the spirit of the more conservative approach as follows.

If the day is missing and the month of the event is the same as the month of the Treatment start date, or falls after this date, it will be assumed that the event occurred after the Treatment start date. Otherwise the event occurred before the Treatment start date. The situation is illustrated in the following diagram.

If the day is missing and the month of the event is the same as the month of the Treatment end date, or falls before this date, it will be assumed that the event occurred before the Treatment end date. Otherwise the event occurred after the Treatment end date. The situation is illustrated in the following diagram.

The analogous approach will be applied for cases when only the year is present.

Technically, this means:

(1) (YYYY-MM)

Onset Date Early = YYYY-MM-01

Onset Date Late = (YYYY-(MM+1)-01 - 1) if MM ≠ 12, else YYYY-12-31

(2) (YYYY)

Onset Date Early = YYYY-01-01

Onset Date Late = YYYY-12-31

It will be considered that an event occurred after the Treatment start date, if

Onset Date Late ≥ Treatment start date

It will be considered that an event occurred before the Treatment end date (+ 30 days), if

Onset Date Early ≤ Treatment end date (+ 30 days)

### 7.7.3. Laboratory Assessments

For both phases, missing dates/times will be handled analogously to AEs in phase two as described in Section [7.7.2](#).

## 7.8. Scheduled vs Unscheduled/ Repeated Assessments

For the data to be presented by the scheduled time-points (visits), only the results of the scheduled assessments as recorded under the corresponding visits will be used. However, for the tables that consider all the post-baseline values (e.g. shift tables) at the same time, the unscheduled assessments will be taken into account as well.

## 7.9. Rules and Formulas for Derived Variables

Time since the original diagnosis, time since the current relapse and time since the last therapy will be calculated with respect to the Treatment start date, i.e.

Treatment start date - Date of the original diagnosis/ the current relapse/ stop date of the last therapy + 1

The responses for all tumor assessments will be derived programmatically as per RECIST 1.1 criteria based on single lesions evaluations.

## 8. Flow of Patients and Specifications of Analyzed Sets

The flow of patients throughout the study will be primarily described based on analysis sets.

### 8.1. Analysis Sets

The following analyses sets are defined.

#### **Enrolled Analysis Set**

All patients to whom a cohort was assigned.

#### **Full Analysis Set (FAS)**

All patients who received at least 1 dose of AK-01, whether or not they completed all protocol requirements.

#### **Dose Limiting Toxicity Assessment Analysis Set**

All patients who

- received at least 1 dose of AK-01 and experienced a DLT; OR
- received  $\geq 38$  doses of AK-01 in Cycle 1 and were not discontinued from the study before completing Cycle 1

#### **PK Analysis Set**

All patients who received at least 1 dose of AK-01 and have PK data that is sufficient and interpretable, as determined by the sponsor.

#### **Efficacy Evaluable Analysis Set**

All patients who completed at least 1 cycle of AK-01 with adequate compliance (i.e.  $\geq 80\%$  and  $\leq 120\%$  of the assigned dose was taken) and had a tumor assessment by RECIST v 1.1 at baseline and at least once following receipt of AK-01.

### 8.2. Protocol Deviations

All protocol deviations will be identified and classified as major/minor before the database lock. No protocol deviations as such will be reasons for exclusion from analysis sets.

### 8.3. Subgroup Analyses

Due to low number of patients, no general subgroup analyses will be performed, unless specified with respect to particular endpoints.

## 9. Statistical Methodology

This section describes the data analysis in details.

### 9.1. General Principles

The IBA internal standard operating procedure "SOP111 Statistical analysis of clinical data" serves as a general guideline on methodology and practical aspects to be considered when carrying out statistical analysis of clinical data. Any data inspection and analyses should take into consideration the principles outlined therein.

Statistical package SAS [4], version 9.4 or higher, will be used for the analysis and for generation of tables, figures and listings (TFL). Statistical package R [5] may be used for creation of specific graphs that will be validated in SAS.

All tables, figures and listings will be presented separately by phase. Further, each table/listing will present the data by cohort, that it by dose cohort in phase I and by tumor type in phase II. The tables related to baseline patient characteristics will include a 'Total' column for phase I patients where appropriate. The efficacy endpoints in phase I will be considered overall (i.e. all dose cohorts combined) and for the MTD cohort only. Efficacy in phase II will be summarized by cohort. The listings will present data by patient. In case the tables and figures summarizing only one subject, the statistic description and visualization would not be useful and the listings will be presented only.

#### 9.1.1. Descriptive Statistics

Unless specified otherwise, the following descriptive statistics will be presented.

Continuous data will be summarized by the total number of non-missing observations, median, min-max, mean, standard deviation.

Categorical data will be described using absolute frequency, relative frequency, and the number of missing values. Relative frequencies will be calculated based on the number of patients in the relevant analysis set or group.

#### 9.1.2. Rounding

The number of decimals used to display the summary tables will be derived from the raw data according to the following rules: mean (geom. mean) +1; standard deviation +2, median +1, min/max +0, coefficient of variation (CV) +2, confidence intervals (CIs) +1.

Percentages in frequency tables will be displayed to one decimal place.

PK parameter data will be presented with 3 significant digits.

### 9.1.3. Missing Data

In general, data imputation to accommodate missing data will not be performed (except missing times and dates, as described in Section 7.7). Censoring for PFS and OS is described in Section 6.1. For safety data, if the causality of an AE is unknown, it will be assumed the event was possibly related to AK-01.

### 9.1.4. Validation of Statistical Programming

There are three levels of validation defined (see the internal IBA SOPs for details):

**Level 1:** Validation by a programmer (author of the program)

**Level 2:** Validation by an independent programmer

**Level 3:** Reprogramming by an independent programmer

Each statistical program will be validated at Level 1 at minimum. In addition, derivations of the primary and secondary endpoints, the safety, efficacy and PK analysis (including TFLs) will be validated at Level 3. If there are any figures produced in R, they must be compared visually by the analogous figures produced in SAS.

Any update of study data performed within the statistical programs (scripts) rather than within the clinical database is called hard coding. Namely, this refers to the cases when subjects or the data are changed (added, removed, corrected, overwritten). The hard coding may NOT be done in any programs. This process ensures integrity of clinical data. In very exceptional situations, when there is no other way how to correct deficiencies in the database, the hard coding may be allowed, if approved by the sponsor. It must be appropriately documented, at minimum in the CSR.

## 9.2. Determination of Sample Size

See the Protocol, Section 3.6.

## 9.3. General Statistical Methodology

### 9.3.1. Proportion

The one-sided exact binomial test for a single proportion  $p$  tests the null hypotheses

$$H_0: p \leq p_0$$

against an alternative

$$H_A: p > p_0.$$

The results will be obtained from a corresponding SAS procedure FREQ, using the following code:

```
PROC FREQ DATA=dataset;  
EXACT BIN;  
TABLES variable / binomial (P=p0 LEVEL="1" EXACT);  
RUN;
```

where `variable` stands for the variable to be tested and "1" denotes success.

### 9.3.2. Kaplan-Meier Analysis

For the Kaplan-Meier analysis of time-to-event data, a corresponding SAS procedure LIFETEST will be utilized, using the following code:

```
PROC LIFETEST DATA=dataset METHOD=KM CONFTYPE=LOGLOG;  
TIME time*event(0);  
STRATA cohort;  
RUN;
```

where

- `time` stands for event and censoring times
- `event` is an event indicator (1=event, 0=censor)
- `cohort` stands for the cohort group variable (if required)
- `CONFTYPE=LOGLOG` specifies log-log transformation used in order to obtain the pointwise confidence intervals of survival estimates based on Greenwood's formula

## 9.4. Patient Disposition, Protocol Deviations and Analysis Sets

Study enrollment (with respect to the Enrolled analysis set) will be presented by site.

The study disposition summary will present:

- Number of patients screened, number of screening failures, number of patients enrolled (Enrolled analysis set)
- Number and percentage of patients who discontinued/completed the study, including reasons

The treatment disposition summary will present:

- Number of patients who received at least 1 dose of AK-01 (Full analysis set)
- Number and percentage of patients who received at least 1 cycle of AK-01
- Number and percentage of patients who discontinued/completed treatment with AK-01, including reasons

Major protocol deviations will be listed by patient and by study center.

## 9.5. Description of Baseline Characteristics

All demographic and other baseline characteristics will be presented for the FAS by cohort and overall in phase I, using the standard sets of summary statistics as defined in Section 9.1.1.

### Demographic Data

Age, sex, ethnicity and race will be summarized and listed.

### Substance Use

Data on tobacco, alcohol and other substances will be listed (ever used, type, current status, duration, amount, unit, frequency).

### Disease Characteristics

Tumor type, type of the specific tumor, time since the original diagnosis, stage of the original diagnosis, time since the current relapse, stage of the current relapse, metastatic/locally advanced disease, sites of metastatic disease and ECOG performance status at baseline will be summarized, all details will be listed.

### Prior Therapy

Regarding systemic therapies, number of regimes, category, best overall response to the last therapy and time since the last therapy will be summarized, all details will be listed. Information on surgical history and prior radiation therapy (yes/no and type) will be provided, all details will be listed.

### Medical History

Medical history will be coded using the MedDRA terminology and will be listed.

## 9.6. Analyses of Efficacy

### 9.6.1. Phase II Primary Objective

The primary endpoint of phase II is ORR. The primary statistical hypotheses

$$H_0: \text{ORR} \leq 0.05$$

will be tested against an alternative

$$H_A: \text{ORR} > 0.05$$

by the means of a one-sided exact binomial test for a single proportion at a significance level of 0.05. See Section 9.3.1 for details on the statistical test. No multiple testing adjustment will be applied. The ORR will be presented with an exact one-sided 95% confidence interval (Clopper & Pearson). The analysis will be performed in the FAS as well as in Efficacy evaluable analysis set. That means, if the analysis set includes patients with missing baseline assessments, non-measurable disease at baseline (though this would be a protocol deviation) or no evaluable post-baseline

assessments, they will be counted in the denominator and not in the numerator. The ORR will be summarized and tested by cohort.

## 9.6.2. Further Efficacy Analyses

ORR rate will be determined also for the phase I data in the FAS as well as in Efficacy evaluable analysis set and will be summarized by cohort and overall. No statistical testing will be performed.

All subsequent efficacy analyses will be performed in Efficacy evaluable analysis set (see Section 8.1 for the definition).

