#### *5.3.2. Evaluable Patients*

Any patient who withdraws from the study before receiving IMP may be replaced.

Any patient in Phase I who is discontinued from the study before completing Cycle 1 or who receives <38 doses of IMP in Cycle 1 will be deemed non-evaluable for DLT assessment at that dose level, unless the patient experiences a DLT. Additional patients may be enrolled to a cohort in Cycle 1 if a patient is withdrawn for reasons other than a DLT (e.g., disease progression, non-compliance, or personal reasons) to ensure that an appropriate number of patients will be evaluated.

Any patient withdrawn for toxicity in Cycle  $\geq 2$  of Phase I will not be replaced.

Any patient withdrawn for toxicity in Phase II prior to completion of Cycle 1 may be replaced.

Any patient who is not evaluable for PK, PD, or biomarkers may be replaced upon consultation with the investigator(s) and the sponsor to ensure collection of sufficient data for interpretation.

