#### Objective Response Rate

Objective response rate (ORR) is defined as a proportion of responders (CR+PR) of those patients whose disease at baseline is assessable by RECIST v 1.1.1.

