#### Disease Control Rate

Disease control rate (DCR) is defined as a proportion of patients with BOR of SD, PR or complete response (CR) of those patients whose disease at baseline is assessable by RECIST v 1.1.1. Confirmation of CR and PR is required, as specified in RECIST v 1.1 guidelines [3], Table 3. The confirmatory scan in such cases must be performed at minimum 4 weeks-5 days, that is 23 days later.

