### Progression Free Survival

Progression free survival (PFS) is defined as the time from the date of first study drug treatment until the date of radiographic documentation of disease progression (as defined by RECIST v 1.1) or death due to any cause, whichever is earlier. Patients without progressive disease or death will be censored at the date of the last adequate tumor assessment. Patients with disease progression or death after missing (or not evaluable)  $\geq 2$  consecutive post baseline tumor assessments will be censored at the date of the last adequate tumor assessment before the missed (or not evaluable) tumor assessments. Technically, events after  $\geq 2$  missing assessments are identified as events that meet either of the following

- there was no preceding post-baseline adequate tumor assessment and the event occurred more than 1 week of the last dose in Cycle 4
- the first post-baseline assessment was performed within 1 week of the last dose in Cycle 2 and then the event occurred more than 10 weeks of the last dose in Cycle 4
- the event occurred more than 19 weeks (2x9 weeks + the allowed assessment window) after the last adequate tumor assessment.

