### Overall Survival (OS)

Overall survival (OS) is defined as the time from the Treatment start date to the date of death due to any cause. Patients without the event will be censored at the Last contact date.

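### SAP 9.6.2 runs BOR, DCR, DOR, PFS and OS only in the Efficacy Evaluable set, so early deaths and unscanned patients drop out of PFS and OS; SAP 9.6.1 tests ORR in two sets and names neither as primary

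*SAP*

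**What the plan says.** **Secondary efficacy set.** SAP 9.6.2, after ORR: "All subsequent efficacy analyses will be performed in Efficacy evaluable analysis set". This covers BOR, DCR, DOR, PFS and OS. SAP 8.1 defines the set as "All patients who completed at least 1 cycle of AK-01 with adequate compliance" (80-120% of the assigned dose) with a RECIST assessment at baseline and at least one after dosing. Protocol 8.1.1 only permits such a restriction; it does not require it.

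**Clocks and events.** In SAP 6.1, PFS runs from the first dose to progression or death from any cause. OS "is defined as the time from the Treatment start date to the date of death due to any cause". One PFS censoring condition is: "there was no preceding post-baseline adequate tumor assessment and the event occurred more than 1 week of the last dose in Cycle 4". By implication, an earlier death with no preceding scan is an event.

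**Primary endpoint.** SAP 9.6.1 tests ORR against 5% with a one-sided exact test at 0.05: "The analysis will be performed in the FAS as well as in Efficacy evaluable analysis set". It counts patients with no evaluable post-baseline scan as non-responders. Protocol 3.6 treats an observed ORR of at least 20%, lasting at least 4 months, as evidence of efficacy and does not say in which set.

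**Replacement.** Protocol 5.3.2: "Any patient withdrawn for toxicity in Phase II prior to completion of Cycle 1 may be replaced".

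**Denominators.** SAP 6.1 defines ORR as a proportion "of those patients whose disease at baseline is assessable by RECIST v 1.1.1". DCR "is defined as a proportion of patients with BOR of SD, PR or complete response (CR) of those patients whose disease" is likewise assessable at baseline. SAP 9.6.1 instead keeps patients without a baseline assessment in the denominator.

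**Censoring.** Protocol 8.2 censors patients not evaluable for PFS and OS at time zero and does not define that group. SAP 6.1 has no such rule, and SAP 9.1.3 points to SAP 6.1 for censoring.

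**The concern.** The evaluable set is defined by what happens after treatment starts. A patient who dies in Cycle 1 is an OS event by definition, yet the analysis set removes that patient. The curves then describe people who completed a cycle and reached a scan, while time is counted from first dose. The SAP also works against its own PFS rule: a death before any post-dose scan should count, but the patient is outside the set, so it never does. No all-treated version of PFS, OS, BOR or DCR is planned.

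DOR is touched only slightly. A FAS responder who fails the compliance condition counts in the FAS ORR but disappears from DOR, and DOR is what informs the 4-month durability criterion.

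For the primary endpoint, two tests with no ranking leave open which result counts. Replacement can widen the gap, because a patient withdrawn for toxicity in Cycle 1 stays in the FAS but cannot be evaluable if no cycle was completed. In an open-label single-arm study, the choice of set could then be made with the results in view.

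**Working it through.** **1. The plan's own figure.** Protocol 3.6 inputs: null 5%, alternative 20%, one-sided exact test, alpha 0.05. The critical count c(n) is the smallest r with P(X ≥ r | n, 0.05) ≤ 0.05. For n=15, c=3, size 0.0362, power 0.602. For n=20, c=4, size 0.0159, power 0.589. Table 2 gives 60% and 59%, so it reproduces. For n=30, c=5, size 0.0156, power 0.745.

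**2. Can the two ORR tests disagree?** Critical counts are 3 for n=10-16, 4 for n=17-28 and 5 for n=29-30. Numbers excluded or replaced are assumptions, and all responders are taken to be evaluable.

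| Situation | FAS | Evaluable set |
|---|---|---|
| 30 treated, 2 not evaluable | 4/30 = 13.3%, p=0.061 | 4/28 = 14.3%, p=0.049 |
| 20 treated, 4 not evaluable | 3/20 = 15.0%, p=0.075 | 3/16 = 18.8%, p=0.043 |
| 15 evaluable, 3 replaced | 3/18 = 16.7%, p=0.058 | 3/15 = 20.0%, p=0.036 |
| 20 evaluable, 3 replaced | 4/23 = 17.4%, p=0.026 | 4/20 = 20.0%, p=0.016 |

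The test flips in the first three rows and the 20% criterion in the last two. In the third row both flip.

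**3. False-positive rate against an all-treated ORR of 5%.** Let the number lost be Binomial(N, q) with q = 10%, 15% or 20% (assumption), with no replacement. The rate is the sum over k of P(k lost) × P(X ≥ c(N−k)), with X ~ Binomial(N−k, p). If every non-evaluable patient is a non-responder, p = 0.05/(1−q), that is 5.6%, 5.9% or 6.3%. If loss is random, p = 0.05.

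| N | FAS | Evaluable, lost all non-responders | Evaluable, random loss |
|---|---|---|---|
| 15 | 3.62% | 3.62-3.64% | 2.05-2.76% |
| 20 | 1.59% | 2.16-4.54% | 1.56-2.51% |
| 30 | 1.56% | 5.06-6.01% | 3.02-3.65% |

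Averaged in this way, the rate passes 5% only at N=30 and only in the adverse case. Part of the gap from the FAS is discreteness of the exact test.

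**4. OS.** The documents give no median; 6 months is assumed. If survival is exponential and deaths before time t are dropped, the reported median is 6 + t. With 30.44 days per month:
- Day 21 (end of Cycle 1): t = 0.69, median 6.69; 7.7% of patients dropped.
- Day 42 (end of Cycle 2): t = 1.38, median 7.38; 14.7% dropped.
- Day 49 (Protocol Appendix 1, note r, allows the scan within 1 week of the last Cycle 2 dose): t = 1.61, median 7.61; 17.0% dropped.

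With the hazard halved for the first 12 weeks (2.76 months, assumption) and the same true median, the later hazard is ln 2/(6 − 1.38) = 0.150 per month. The shift is then t/2, giving 6.34 at day 21 and 6.80 at day 49.

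**5. PFS.** If a share e of treated patients is dropped and all were early events (assumption), the reported median is the time at which the FAS curve equals 0.5 × (1−e). For e = 3/30 that is 0.45, and the exponential ratio is log2(1/0.45) = 1.15. For e = 6/30 it is 0.40 and the ratio is 1.32. Patients excluded alive and unscanned cause no shift, because they have no follow-up time for PFS.

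**6. DCR.** Assume 12 of 30 have disease control and none of these is excluded: 12/30 = 40.0%, 12/27 = 44.4%, 12/24 = 50.0%.

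**The case against.** Protocol 8.1.1 allows the restriction, and the SAP uses that option openly with a defined set. The affected endpoints are exploratory, untested and from a single-arm study of preliminary efficacy. This stands and limits the seriousness, but permission does not make a curve that starts at first dose and omits early deaths an all-treated estimate.

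Four stronger readings are tempting and not supported:
- *No all-treated efficacy analysis exists.* ORR is analysed in the FAS in both phases, and in Phase II unscanned patients count as non-responders.
- *Early deaths are hidden.* SAP 9.8 and 9.8.2 tabulate deaths as safety data in the FAS. That does not correct a Kaplan-Meier curve, but the deaths are reported.
- *Compliance must be met in Cycle 1.* SAP 8.1 says at least one cycle, so a patient who was non-compliant in Cycle 1 may qualify later. Only deaths and withdrawals before completing Cycle 1 are certainly out.
- *Type I error is generally inflated.* Against its own null, the evaluable-set test holds its level. The excess needs an all-treated null, N=30 and every non-evaluable patient a non-responder.

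Scans at discontinuation (Protocol 6.7.1) keep some early leavers in the set, so the day 49 figure is a pessimistic illustration. It is not a strict bound either, since missed scans and patients who leave alive in Cycle 1 and die later are not modelled. The compliance condition can also occasionally act in the opposite direction.

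**Conclusion.** Both parts hold on the text. PFS and OS will omit treated patients who die or stop in Cycle 1 or have no post-dose scan, and BOR and DCR are restricted in the same way. The tendency is upward. A 6-month OS median reads about 6.7 to 7.6 months under an exponential curve, or 6.3 to 6.8 with a halved early hazard. DOR is affected only through responders who fail compliance. For ORR, the two unranked tests can give opposite verdicts at planned cohort sizes, and the 20% criterion can flip with them.

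The reading of the documents is secure. The sizes rest on assumed loss, replacement, survival and response patterns, because the documents give none. The point deserves correction but does not invalidate the primary endpoint, for which a sound FAS analysis is already planned.

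**What to change.** - **SAP 9.6.1:** name the FAS as the only set for the formal ORR test and for reading the 20% criterion of Protocol 3.6. Report the evaluable set as an untested sensitivity estimate.
- **SAP 9.6.2:** analyse BOR, DCR, PFS and OS in the FAS under the event and censoring rules of SAP 6.1, so that a death before the first scan counts as those rules intend. Analyse DOR in all FAS responders. Keep the evaluable set as sensitivity.
- **SAP 6.1, BOR and DCR:** add a not-evaluable BOR category for patients without a post-dose scan, which the SAP now lacks, and count them as without disease control.
- **SAP 6.1, ORR and DCR:** align the denominators with SAP 9.6.1.
- **Protocol 8.2:** reconcile censoring at time zero with SAP 6.1, which SAP 9.1.3 already names as the place for the censoring rules.

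The cost is wording, with no new data, and it should be settled before database lock. DCR, PFS and OS would probably look slightly less favourable, and a positive ORR test in the evaluable set alone could not be claimed. With the FAS as sole set, a cohort of 30 needs 5 responders (power 74% at a true ORR of 20%).
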